## 8.3.1.1. Reporting SAEs to Pfizer Safety

All SAEs occurring in a participant during the active collection period as described in Section 8.3.1 are reported to Pfizer Safety on the CT SAE Report Form immediately upon awareness and under no circumstance should this exceed 24 hours, as indicated in Appendix 3. The investigator will submit any updated SAE data to the sponsor within 24 hours of it being available.

#### 8.3.1.2. Recording Nonserious AEs and SAEs on the CRF

All nonserious AEs and SAEs occurring in a participant during the active collection period, which begins after obtaining informed consent as described in Section 8.2.1, will be recorded on the AE section of the CRF.

The investigator is to record on the CRF all directly observed and all spontaneously reported AEs and SAEs reported by the participant.

## 8.3.2. Method of Detecting AEs and SAEs

The method of recording, evaluating, and assessing causality of AEs and SAEs and the procedures for completing and transmitting SAE reports are provided in Appendix 3.

Care will be taken not to introduce bias when detecting AEs and/or SAEs. Open ended and nonleading verbal questioning of the participant is the preferred method to inquire about AE occurrences.

#### 8.3.3. Follow-up of AEs and SAEs

After the initial AE/SAE report, the investigator is required to proactively follow each participant at subsequent visits/contacts. For each event, the investigator must pursue and obtain adequate information until resolution, stabilization, the event is otherwise explained, or the participant is lost to follow-up (as defined in Section 7.3).

In general, follow-up information will include a description of the event in sufficient detail to allow for a complete medical assessment of the case and independent determination of possible causality. Any information relevant to the event, such as concomitant medications and illnesses, must be provided. In the case of a participant death, a summary of available autopsy findings must be submitted as soon as possible to Pfizer Safety.

Further information on follow-up procedures is given in Appendix 3.

# 8.3.4. Regulatory Reporting Requirements for SAEs

Prompt notification by the investigator to the sponsor of an SAE is essential so that legal obligations and ethical responsibilities towards the safety of participants and the safety of a study intervention under clinical investigation are met.

The sponsor has a legal responsibility to notify both the local regulatory authority and other regulatory agencies about the safety of a study intervention under clinical investigation. The sponsor will comply with country specific regulatory requirements relating to safety reporting to the regulatory authority, institutional review boards (IRBs)/ethics committees (ECs), and investigators.

Investigator safety reports must be prepared for suspected unexpected serious adverse reactions (SUSARs) according to local regulatory requirements and sponsor policy and forwarded to investigators as necessary.

An investigator who receives an investigator safety report describing an SAE or other specific safety information (eg, summary or listing of SAEs) from the sponsor will review and then file it along with the with the SRSD(s) for the study and will notify the IRB/EC, if appropriate according to local requirements.

# 8.3.5. Exposure During Pregnancy or Breastfeeding, and Occupational Exposure

Exposure to the investigational product under study during pregnancy and occupational exposure are reportable to Pfizer Safety within 24 hours of investigator awareness.

# **8.3.5.1.** Exposure During Pregnancy

Details of all pregnancies in female partners of male participants will be collected after the start of study intervention and until 28 days after the last dose.

If a pregnancy is reported, the investigator should inform the sponsor within [24 hours] of learning of the pregnancy and should follow the procedures outlined in Appendix 4.

Abnormal pregnancy outcomes (eg, spontaneous abortion, fetal death, stillbirth, congenital anomalies, ectopic pregnancy) are considered SAEs.

#### 8.3.5.2. Exposure During Breastfeeding

An exposure during breastfeeding occurs if:

A female is found to be breastfeeding while being exposed or having been exposed to study intervention (ie, environmental exposure). An example of environmental exposure during breastfeeding is a female family member or healthcare provider who reports that she is breastfeeding after having been exposed to the study intervention by inhalation or skin contact.

The investigator must report exposure during breastfeeding to Pfizer Safety within 24 hours of the investigator's awareness, irrespective of whether an SAE has occurred. The information must be reported using the CT SAE Report Form. When exposure during breastfeeding occurs in the setting of environmental exposure, the exposure information does not pertain to the participant enrolled in the study, so the information is not recorded on a CRF. However, a copy of the completed CT SAE Report Form is maintained in the investigator site file.

## 8.3.5.3. Occupational Exposure

An occupational exposure occurs when, during the performance of job duties, a person (whether a healthcare professional or otherwise) gets in unplanned direct contact with the product, which may or may not lead to the occurrence of an AE.

An occupational exposure is reported to Pfizer Safety within 24 hours of the investigator's awareness, using the CT SAE Report Form, regardless of whether there is an associated SAE. Since the information does not pertain to a participant enrolled in the study, the information is not recorded on a CRF; however, a copy of the completed CT SAE Report Form is maintained in the investigator site file

#### 8.3.6. Cardiovascular and Death Events

Any cardiovascular events and deaths will be assessed on a case by case basis through duration of the study.

# 8.3.7. Disease-Related Events and/or Disease-Related Outcomes Not Qualifying as AEs or SAEs

The following disease-related events (DREs) are common in participants with hemophilia A or B and can be serious/life threatening:

• Bleeding, pain, swelling, or decreased range of motion due to a bleed

Certain events, due to the participant's hemophilia, will be recorded as a DRE. Investigators

should determine if an event is expected because of the participant's hemophilia. But bleeding or bruising, not due to paticipants' hemophilia, should be recorded as an AE, not a DRE. Because these events are typically associated with the disease under study, they will not be reported according to the standard process for expedited reporting of SAEs even though the event may meet the definition of a SAE. These events will be recorded on the SAE CRF page in the participant's CRF within 24 hours.

NOTE: However, if either of the following conditions applies, then the event must be recorded and reported as an SAE (instead of a DRE):

• The event is, in the investigator's opinion, of greater intensity, frequency, or duration than expected for the individual participant.

OR

• The investigator considers that there is a reasonable possibility that the event was related to study intervention.

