#### **Potential Risks**

Individuals may experience risks or discomforts at the anatomical site of SC injection with PF-06741086. Injection Site Reactions, which may include pain, swelling, bruising, induration, and hematoma, are considered adverse drug reactions for PF-06741086.

Potential risks for treatment with PF-06741086 are thrombi or emboli. Depending on location and severity, thrombi or emboli may be life threatening or fatal.

Because PF-06741086 is a fully human IgG1 with no endogenous counterpart, the anti-drug antibody response (ADA) is expected to primarily affect the PK, efficacy and/or measurement of PF-06741086. An additional potential immunogenicity risk is the ADA-induced hypersensitivity. Therefore, individuals with a diagnosis or history of thrombotic or ischemic disease (including myocardial infarction, deep venous thrombosis or pulmonary embolism), individuals with coronary artery disease and individuals with an allergy to hamster protein should be excluded from study participation.

More detailed information about the known and expected benefits and risks and reasonably expected adverse events (AEs) of PF-06741086 may be found in the investigator's brochure (IB), which is the single reference safety document (SRSD) for this study.

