## Type of Participant and Disease Characteristics:

- 2. Participants with a diagnosis of severe hemophilia A or B (FVIII or FIX activity <1%, respectively).
- 3. Participants without inhibitor must also meet the following criteria:
  - No detectable or documented history of inhibitors (≥0.6 BU/mL or greater than the upper limit of normal [ULN] for the testing laboratory) against FVIII or FIX prior to enrollment.
  - Participants with on-demand treatment regimen with ≥6 acute bleeding episodes (spontaneous and/or traumatic) that required coagulation factor infusion during the 4 months period prior to Screening and willing to continue to receive on-demand treatment during the study. Surgical bleeding episodes do not apply to this criterion.
- 4. Participants with inhibitor must also meet the following criteria:

- Documentation of current high titer inhibitor (≥5 BU/mL) or current low titer inhibitor (<5 BU/mL) refractory to FVIII or FIX replacement and with FVIII or FIX recovery <60% of expected within previous 4 months prior to screening.
- Participants with on-demand treatment regimen with ≥6 bleeding episodes (spontaneous and/or traumatic) necessitating treatment with bypass factor for at least 4 months prior to screening and willing to continue to receive on-demand treatment during the study. Surgical bleeding episodes do not apply to this criterion.

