#### Assessment of Intensity

The investigator will make an assessment of intensity for each AE and SAE reported during the study and assign it to 1 of the following categories:

Mild: An event that is easily tolerated by the participant, causing minimal discomfort and not interfering with everyday activities.

Moderate: An event that causes sufficient discomfort and interferes with normal everyday activities.

Severe: An event that prevents normal everyday activities. An AE that is assessed as severe should not be confused with an SAE. Severe is a category utilized for rating the intensity of an event; and both AEs and SAEs can be assessed as severe.

An event is defined as "serious" when it meets at least 1 of the predefined outcomes as described in the definition of an SAE, NOT when it is rated as severe.

GRADE	Clinical Description of Severity
1	MILD adverse event
2	MODERATE adverse event
3	SEVERE adverse event
4	LIFE-THREATENING consequences; urgent intervention indicated
5	DEATH RELATED TO adverse event

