## **Assessment of Causality**

- The investigator is obligated to assess the relationship between study intervention and each occurrence of each AE/SAE.
- A "reasonable possibility" of a relationship conveys that there are facts, evidence, and/or arguments to suggest a causal relationship, rather than a relationship cannot be ruled out.
- The investigator will use clinical judgment to determine the relationship.
- Alternative causes, such as underlying disease(s), concomitant therapy, and other risk factors, as well as the temporal relationship of the event to study intervention administration will be considered and investigated.

- The investigator will also consult the investigator's brochure (IB) and/or product information, for marketed products, in his/her assessment.
- For each AE/SAE, the investigator must document in the medical notes that he/she has reviewed the AE/SAE and has provided an assessment of causality.
- There may be situations in which an SAE has occurred and the investigator has minimal
  information to include in the initial report to the sponsor. However, it is very important
  that the investigator always make an assessment of causality for every event before
  the initial transmission of the SAE data to the sponsor.
- The investigator may change his/her opinion of causality in light of follow-up information and send an SAE follow-up report with the updated causality assessment.
- The causality assessment is one of the criteria used when determining regulatory reporting requirements.
- If the investigator does not know whether or not the investigational product caused the event, then the event will be handled as "related to investigational product" for reporting purposes, as defined by the sponsor. In addition, if the investigator determines that an SAE is associated with study procedures, the investigator must record this causal relationship in the source documents and CRF, and report such an assessment in the dedicated section of the CT SAE Report Form and in accordance with the SAE reporting requirements.

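### Protocol 8.3.7 makes a worse-than-usual or possibly drug-related hemophilia bleed an SAE with no seriousness test, in conflict with Appendix 3

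*Protocol*

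**What the plan says.** Protocol 8.3.7 lists bleeding, and pain, swelling or loss of motion from a bleed, as DREs when they are due to the participant's hemophilia. It exempts them from expedited SAE reporting and then adds: "These events will be recorded on the SAE CRF page", within 24 hours. No seriousness limit is stated, although the section says only that such events can be serious and may meet the SAE definition.

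A NOTE then names two exceptions. The first is: "The event is, in the investigator's opinion, of greater intensity, frequency, or duration than expected for the individual participant". The second is: "The investigator considers that there is a reasonable possibility that the event was related to study intervention". If either applies, "then the event must be recorded and reported as an SAE (instead of a DRE"). The section's only AE route is for bleeding or bruising that is not due to hemophilia.

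Appendix 3 works differently. Section 10.3.2 defines an SAE by outcomes a to f. Section 10.3.3 says an event is serious "when it meets at least 1 of the predefined outcomes as described in the definition of an SAE", and not because it is rated severe. Its recording table puts every non-serious AE on the CRF and none on the CT SAE Report Form.

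**The concern.** Neither NOTE condition is a seriousness criterion. One compares the bleed with the participant's usual pattern; the other is a causality judgment. A non-serious joint bleed judged possibly related to study drug therefore has two classifications, depending on which section the site follows.

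The frequency, severity and causality of TEAEs from Day 1 to Day 42 is a primary endpoint (protocol section 3; SAP 3.1). Following 8.3.7 to the letter would put non-serious bleeds into the SAE count and would leave no stated way to count them as non-serious TEAEs. The SAP does not settle the matter. Its TEAE definition (3.5.1) and safety analysis (6.1) say nothing about DREs, and its bleeding summary (6.5.4) gives number and type but neither causality nor seriousness.

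**Working it through.** The plan states no figure on this point, so there is none to reproduce. The check is a comparison of text, followed by arithmetic on how often the conflict could arise.

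**1. The same event under each section.** Take a non-serious bleed due to hemophilia.

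| Situation | Protocol 8.3.7 | Appendix 3 (10.3.1 to 10.3.3) |
|---|---|---|
| Worse or more frequent than usual | SAE | No longer excluded as an expected disease sign, or counted as an exacerbation of a preexisting condition: AE. Not an SAE without an outcome a to f |
| Reasonably possibly drug-related | SAE | Causality is assessed separately from seriousness: non-serious AE |
| Neither | DRE, on the SAE CRF page | Expected sign of the disease: not an AE |

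Someone might argue that a drug-related bleed of ordinary severity stays excluded from the AE definition as a disease sign. That does not help 8.3.7, because 10.3.2 says an event that is not an AE cannot be an SAE. On no reading does Appendix 3 make either condition sufficient for an SAE.

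**2. How many bleeds to expect.** Protocol 5.1 requires at least 6 bleeds "that required coagulation factor infusion during the 4 months period prior to Screening" for participants without inhibitors, and sets a similar minimum for those with inhibitors.

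- Daily rate: 6 / (4 × 365.25/12) = 6 / 121.75 = 0.0493
- Per participant over 42 days: 0.0493 × 42 = 2.07
- Six participants: 2.07 × 6 = 12.4

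This counts all bleeds at the minimum entry rate with no drug effect. It is not the number that meets a NOTE condition.

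**3. Chance that the NOTE is triggered at least once.** The documents give neither the reduction in bleeding nor the share q of bleeds meeting a condition, so both are assumed over a range. With m expected bleeds and Poisson counts, P(at least one) = 1 − exp(−m·q). For example, 12.42 × 0.05 = 0.62 gives 46%.

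| Assumed reduction | m | q = 5% | q = 10% | q = 20% |
|---|---|---|---|---|
| 0% | 12.4 | 46% | 71% | 92% |
| 50% | 6.2 | 27% | 46% | 71% |
| 80% | 2.5 | 12% | 22% | 39% |

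Some of these bleeds could be genuinely serious, so for a given q these are upper limits on the chance of a misclassification.

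**4. Effect on the SAE rate.** One participant wrongly counted moves it from 0/6 (0%; exact 95% interval 0 to 45.9%) to 1/6 (16.7%; 0.4 to 64.1%).

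**The case against.** The best defence is that the NOTE applies only to DREs that already meet the SAE definition. It follows the sentence that exempts DREs from expedited reporting even if they do, so it can be read as restoring SAE reporting for those events while Appendix 3 still governs seriousness. The reading is plausible, but the limit is not written. If it was intended, 8.3.7 is silent on the non-serious bleed that meets a condition, and the same sentence is needed.

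A second defence is that a drug-related bleed can be called not due to hemophilia and so use the section's AE route. The text does not say this, and the NOTE sends a possibly related DRE to SAE status instead.

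It is also fair to say that bleeds are not lost, since SAP 6.5.4 summarises them from Day 1 to Day 42. No hypothesis, threshold or decision rule depends on the SAE rate, and the error is towards over-reporting. These points stand and limit the size of the problem.

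A reader might infer more than the documents support:

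- **Unknown causality.** Appendix 3 has a clause beginning "If the investigator does not know whether or not the investigational product caused the event", under which the event is handled as related for reporting. It does not follow that every bleed of unknown cause becomes an SAE. The NOTE needs a positive judgment, and Appendix 3 defines a reasonable possibility as more than being unable to exclude a relationship.
- **Injection-site hematoma.** Section 2.3 says "Injection Site Reactions, which may include pain, swelling, bruising, induration, and hematoma, are considered adverse drug reactions". These reactions have their own primary endpoint, Schedule of Activities row and CTCAE grading, so there is no good ground to expect them to be filed as DREs.
- **Masking of a thrombotic SAE.** Nothing supports this. With six participants events can be read individually, and cardiovascular events are assessed case by case (8.3.6).
- **Twelve SAEs.** Recording on the SAE page is not the same as SAE status.

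**Conclusion.** The conflict is real on the plain wording. For a hemophilia-type bleed that is worse than usual or reasonably possibly drug-related, 8.3.7 requires an SAE with no seriousness condition, while Appendix 3 makes the same non-serious event a non-serious AE.

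The consequence is an SAE count that can be inflated and a non-serious TEAE count that can be short, in a primary endpoint observed in six people. A single affected participant is worth 16.7 percentage points. How often this would happen cannot be settled from the documents: the 12 expected bleeds assume the minimum entry rate and no drug effect, and the 5% to 20% share is an assumption. No power or alpha figure is affected. The point deserves correction because the classification should not depend on which section a site consults.

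**What to change.** Reconcile 8.3.7 with 10.3:

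- State that an event meeting either NOTE condition is recorded as an AE, and so counts as a TEAE, and is recorded and reported as an SAE only if it also meets a criterion in 10.3.2.
- Limit the SAE-page and 24-hour rule to DREs that meet a seriousness criterion. Other DREs stay on the bleeding-episode record, which the Schedule of Activities already collects from screening to Day 42.

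The cost is a wording change in 8.3.7 and in the CRF completion guideline. No new data are collected, clinical management does not change, and sites complete fewer expedited forms.

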# 8.3.8. Adverse Events of Special Interest

Not applicable.

#### 8.3.9. Medical Device Deficiencies

Medical devices are being provided for use in this study as a prefilled syringe for the purposes of administering study intervention. In order to fulfill regulatory reporting obligations worldwide, the investigator is responsible for the detection and documentation of events meeting the definitions of device deficiency that occur during the study with such devices.

The definition of a medical device incident can be found in Appendix 8.

NOTE: Deficiencies fulfilling the definition of an AE/SAE will also follow the processes outlined in Section 8.3.1 through 8.3.4 and Appendix 3 of the protocol.

#### **8.3.9.1.** Time Period for Detecting Medical Device Incidents

Medical device deficiencies of the device that result in an incident will be detected, documented, and reported during all periods of the study in which the medical device is used.

If the investigator learns of any device deficiency at any time after a participant has been discharged from the study, and such incident is considered reasonably related to a medical device provided for the study, the investigator will promptly notify the sponsor.

The method of documenting medical device incidents is provided in Appendix 8.

## 8.3.9.2. Follow-up of Medical Device Deficiencies

Follow-up applies to all participants, including those who discontinue study intervention.

The investigator is responsible for ensuring that follow-up includes any supplemental investigations as indicated to elucidate the nature and/or causality of the incident.

New or updated information will be recorded on a follow-up form with all changes signed and dated by the investigator.

#### 8.3.9.3. Prompt Reporting of Device Deficiencies to Sponsor

Device deficiencies will be reported to the sponsor within 1 day after the investigator determines that the event meets the protocol definition of a medical device deficiency. Information will be provided to the sponsor as described in the IP Manual.

Any device deficiency that is associated with an SAE must be reported to Pfizer Safety within 24 hours upon the investigator's awareness as outlined in Section 8.3.1.1 and 8.3.1.2.

The sponsor will be the contact for the receipt of device deficiency information.

## 8.3.9.4. Regulatory Reporting Requirements for Device Deficiencies

The investigator will promptly report all device deficiencies occurring with any medical device provided for use in the study in order for the sponsor to fulfill the legal responsibility to notify appropriate regulatory authorities and other entities about certain safety information relating to medical devices being used in clinical studies.

The investigator, or responsible person according to local requirements (eg, the head of the medical institution), will comply with the applicable local regulatory requirements relating to the reporting of device deficiencies to the IRB/EC.

